2.5 Analysis of the primary objective

2.5.1 Primary endpoint

The primary endpoint is the achievement of at least a 50% reduction from baseline in monthly migraine days in the last month (month 3) of the Double-Blind Treatment Epoch.

The primary analysis will contrast active investigational drug versus placebo in the FAS.

2.5.2 Statistical hypothesis, model, and method of analysis

The following hypothesis refers to alternative hypothesis. For tests of superiority, null hypothesis presuppose no difference between the treatment groups with respect to the parameter of interest.

Primary hypothesis

- The active treatment arm group is superior to placebo with regard to the proportion of patients who achieve at least a 50% reduction from baseline in monthly migraine days in the last month (month 3) of the Double-Blind Treatment Epoch;

$$H_1: \theta_1 > 1$$

where θ_1 is the odds ratio of active over corresponding placebo.

The primary analyses will compare the 50% response rate, which is defined as the proportion of patients who achieve at least a 50% reduction from baseline in monthly migraine days in the last month (month 3) of the Double-Blind Treatment Epoch, between AMG 334 vs placebo. Patients with missing monthly migraine days' data at month 3 of the double-blind treatment epoch will be imputed as non-responders.

A Cochran-Mantel-Haenszel (CMH) test stratified by the migraine frequency (4-7 and 8-14 monthly migraine days strata) will be used under a significance level of 0.025, one-sided (0.05, two-sided) to evaluate the association between the 50% responder rate and the treatment. The estimated common odds ratio, 95% confidence intervals and two-sided p-values will be reported.

Additionally, the estimated common relative risk and risk difference with their asymptotic (Wald) confidence limits will be provided.

2.5.3 Sensitivity analyses

In order to assess the robustness of the analysis for primary endpoint during the double-blind treatment epoch, next analyses will be done:

1. Without any imputation for missing data, a generalized linear mixed model (GLMM) which account for temporal variability will be used.
2. Logistic regression analysis will be used to get odds ratio of AMG 334 vs placebo in the 50% response rate after the missing data are imputed as non-response.
3. Stratified CMH test will be repeated based on multiple imputation with assumption of MAR and MNAR.

In all cases, the odds ratio of treatment group compared to placebo group with associated 95% confidence intervals and p-values will be provided.

All details of models descriptions are in [Section 5.4.1](#).

To address the impact of missing data on primary efficacy analysis, the amount of missing data, the distribution of missing data among treatment groups, and the reasons for missing data will be examined. If substantial amount of missing data is observed or if imbalance occurs amongst the treatment groups, additional sensitivity analyses, including those based on alternative missing data assumptions, will be performed as deemed appropriate and necessary.

2.6 Analysis of secondary efficacy objectives

2.6.1 Secondary endpoints

The secondary endpoints during double-blind treatment epoch are:

- Change from baseline in monthly migraine days in the last month (month 3) of the double-blind treatment epoch
- Change from baseline in “impact on everyday activities” domain as measured by the MPFID in the last month (month 3) of the double-blind treatment epoch
- Change from baseline in “physical impairment” domain as measured by the MPFID in the last month (month 3) of the double-blind treatment epoch
- Change from baseline in acute monthly migraine-specific treatment days in the last month (month 3) of the double-blind treatment epoch
- The achievement of at least a 75% reduction from baseline in monthly migraine days in the last month (month 3) of the double-blind treatment epoch
- The achievement of a 100% reduction from baseline in monthly migraine days in the last month (month 3) of the double-blind treatment epoch

2.6.2 Statistical methods of analyses

Analysis of secondary efficacy endpoints will utilize the FAS. Subjects will be analyzed according to their randomized treatment group regardless of the actual treatment received during the study.

For efficacy analysis at week 12, the continuous change from baseline efficacy endpoints will be analyzed using a linear mixed effects model including treatment group, baseline value, stratification factor, scheduled visit, and the interaction of treatment group with scheduled visit, without any imputation for missing data.

The dichotomous secondary efficacy endpoints derived from corresponding continuous endpoints will be analyzed using the stratified Cochran-Mantel-Haenszel (CMH) test after the missing data are imputed as non-response.

In all cases, estimates (difference/or odds ratio) of treatment group compared to placebo group with associated 95% confidence intervals and p-values will be provided. Additionally, the estimated common relative risk and risk difference with their asymptotic (Wald) confidence limits will be provided for the dichotomous secondary efficacy variables.

2.6.3 Sensitivity analyses

The following sensitivity analyses will be provided:

Analysis of continuous efficacy variables will be repeated using an analysis of covariance (ANCOVA) model including treatment group and stratification factor as fixed effects in the model with baseline value as covariate. Missing data at Week 12 will be imputed using its baseline value (BOCF). In addition, multiple imputation (MI) techniques applying missing at random (MAR) and missing not at random (MNAR) approaches will be used to assess the impact of missing values on the interpretation of the results for the double-blind treatment epoch (the models descriptions are in [Section 5.4.2](#)).

Analysis of dichotomous efficacy endpoints which are derived from corresponding continuous endpoints will be repeated using the GLMM and logistic regression as in [Section 2.5.3](#). In all cases, estimates (difference/or odds ratio) of treatment group compared to placebo group with associated 95% confidence intervals and p-values will be provided.

Detailed primary and secondary efficacy analysis methods, sensitivity analyses, and covariates included in the models are summarized in the table below.

Table 5 Summary of Efficacy Endpoints and Analysis Methods during DBTE

Endpoint	Primary Summary and Analysis Method	Sensitivity Analysis

Primary: The achievement of at least a 50% reduction from baseline in monthly migraine days in the last month (4 weeks of the 12-week) of the double-blind epoch
	
Analysis Method I:
 
 1. Summary statistics by visit using observed data 2. A stratified Cochran-Mantel-Haenszel (CMH) test will be used after the missing data are imputed as non-response 3. Additional analysis to estimate relative risk and risk difference. 	
Analysis Method II: Without any imputation for missing data, adjusted odds ratios from a generalized linear mixed model that includes treatment group, baseline migraine days, stratification factor, scheduled visit, and the interaction of treatment and scheduled visit using observed data with unstructured (UN) covariance matrix structure, and using responder rate calculated using mean monthly migraine days
 
Analysis method III, NRI: analyze using a logistic regression model that includes treatment and stratification factor as fixed effects and baseline migraine

		
days as covariate
 
Analysis Method I:
 
A stratified Cochran-Mantel-Haenszel (CMH) test will be used after the missing data are imputed with assumption of MAR and MNAR

Secondary:
 
Change from baseline in monthly migraine days in the last month of the double-blind epoch
	
Analysis method IV:
 
 1. Summary statistics by visit using observed data 2. Least squares mean at each timepoint calculated based on a linear mixed effects model including treatment group, baseline value, stratification factor, scheduled visit, and the interaction of treatment group with scheduled visit using observed data. Unstructured covariance matrix structure will be used. 3. Test treatment difference using a contrast from the model above. 	
Analysis method V:
 
ANCOVA Analysis for missing data are imputed as baseline (BOCF)
 
Analysis method VI:
 
MI with assumption of MAR and MNAR (control-based pattern imputation and treatment effect adjusted imputation)

Change from baseline in monthly physical impairment scores as measured by MPFID in the last month of the double-blind epoch
	
Analysis method IV.
	

Change from baseline in monthly impact on everyday activities as measured by MPFID in the last month of the double-blind epoch
	
Analysis method IV.
	

Change from baseline in monthly acute migraine-specific medication treatment days in the last month of the double-blind epoch
	
Analysis method IV.
	

The achievement of at least a 75% reduction from baseline in monthly migraine days in
	
Analysis Method I.
	

the last month of the double-blind epoch		
The achievement of a 100% reduction from baseline in monthly migraine days in the last month of the double-blind epoch	Analysis Method I.	

2.6.4 Subgroup analyses

The primary and secondary efficacy endpoints will be analyzed at week 12 for the following subgroups that defined by categorical variables at baseline:

- Monthly migraine days per stratification factor (4-7 vs 8-14)
- Age (< median vs ≥ median)
- Sex (Male vs Female)

The effect of other explanatory variables, maybe investigated with respect to the primary and secondary efficacy analyses if, upon clinical review, differences between treatment groups are deemed clinically meaningful.

The subgroup analysis will be assessed for the primary and secondary efficacy endpoints using primary analysis method and presented at Week 12. For continuous variables the interaction p-value will be defined from modified primary model with additional terms of subgroup and subgroup by treatment group interaction as two additional effects. However, for subgroup of dichotomous variables, the interaction p-value will come from Logistic regression that includes treatment group, stratification factor, subgroup factor and treatment by subgroup factor interaction as fixed effect with baseline value as covariate.

If the value of the group variable cannot be determined, the subject will be excluded from the corresponding subgroup analysis. For each subgroup analysis, if, in any treatment group, the number of subjects is less than 10 for a subgroup, then the summary for that subgroup will be displayed but will not be included in tests for subgroup-by-treatment interaction when the test is based on categorical subgroups (when the test is based on a continuous variable, the subject data will be included).

The adjusted mean changes from baseline, SE's, and 95% CIs for each subgroup and the nominal p-value for subgroup by treatment interaction will be calculated.

2.7 Safety analyses

For safety endpoints, all randomized subjects who received at least one dose of investigational product (ie, utilizing the SAF for DBTE will be analyzed based on the randomized treatment unless a subject has received the incorrect dose the entire period of interest (phase or study).

No statistical testing comparing treatment groups will be performed in the safety analyses.

2.7.1 Adverse events (AEs)

The Medical Dictionary for Regulatory Activities (MedDRA) version 18.0 or later will be used to code all adverse events (AE) to a system organ class (SOC) and a preferred term (PT). All adverse events will be graded using the Common Terminology Criteria for Adverse Events (CTCAE) Version 4.03 (see details in [Section 5.2](#)). All adverse event tables will be summarized by treatment group.

AE tables by SOC and PT (and grade), will be sorted alphabetically by SOC and then descending order of frequency based on the AMG 334 140 mg dose by PT within each SOC. AE tables by preferred term only will be sorted in descending order of frequency based on the AMG 334 140 mg dose, then the placebo dose and then alphabetically.

Overall subject incidence of AEs will be summarized for all treatment-emergent AEs (TEAEs), serious AEs, AEs leading to withdrawal of IP, and fatal AEs for the DBTP.

Subject incidence of all TEAEs, serious AEs, AEs leading to withdrawal of IP, serious AEs leading to withdrawal of IP, fatal AEs will be tabulated by SOC and PT for the DBTE.

In addition, subject incidence of all treatment-emergent AEs and serious AEs will be tabulated by SOC, PT and CTCAE grade for the DBTE.

Subject incidence and exposure-adjusted subject incidence of all TEAEs and serious AEs will be tabulated by PT in descending order of frequency for the DBTE.

Treatment-related treatment-emergent AEs will be summarized for DBTE by SOC, PT and CTCAE grade.

2.7.2 Laboratory data

Summary statistics will be presented for absolute as well as change from baseline of laboratory haematology, blood chemistry results over time by treatment and laboratory test category.

Summary of change from baseline for absolute neutrophil count (ANC), alanine transaminase (ALT) and aspartate aminotransferase (AST) will also be provided for entire study.

Additional liver test summary table will provide the number and percentage of subjects by following categories:

- AST and ALT ($> 3x$ ULN; $> 5x$ ULN; $> 10x$ ULN; $> 20x$ ULN respectively)
- ALT/AST $> 3x$ ULN and Total Bili $> 2x$ ULN and ALP $\leq 2x$ ULN
- ALT/AST $> 3x$ ULN and Total Bili $> 2x$ ULN and ALP $> 2x$ ULN

2.7.3 Columbia-Suicide Severity Rating Scale (C-SSRS)

No statistical testing will be performed on C-SSRS. The number and percentage of subjects reporting any suicidal ideation and any suicidal behavior will be summarized descriptively by treatment group for DBTE. Shift table of C-SSRS maximum severity of suicidal ideation/behavior compared to baseline will be provided by treatment group for DBTE.

2.7.4 Electrocardiogram (ECG)

The ECG measurements from this clinical study were performed as per standard of care for routine safety monitoring, rather than for purposes of assessment of potential QTc effect. Subject incidence of abnormal ECG diagnosis will be summarized by treatment group separately for the DBTE. However, since these evaluations may not necessarily be performed under the rigorous conditions expected to lead to meaningful evaluation of QTc data, these data are not expected to be useful for meta-analysis with data from other trials.

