5.5.4 Instructions for prescribing and taking study treatment

Subcutaneous (s.c.) injections are to be given for each investigational product administration. For purposes of study treatment dosing, “q.m.” refers to an every 4 weeks injection regimen. The study drug administration date should be in 4 week increments (+/- 5 days) from the first dose of study drug. Any dose administrations that may occur greater than +/- 5 days from the 4 week time point (e.g., patient unavailability) should be discussed with the Sponsor prior to dosing. The anatomical sites for administration of investigational product are the upper arm, upper thigh, or abdomen; the location of the injection sites should be documented in the source document.

Double-Blind Treatment Epoch:

Two injections of AMG 334 70 mg (equaling 140 mg total dose) or placebo will be administered by qualified study staff at each dosing visit during the 12-week double-blind treatment epoch (i.e., at Day 1 and Weeks 4 and 8).

Open-label Treatment Epoch and PTA-Open-Label Treatment Epoch:

Two injections of open-label AMG 334 70 mg (equaling 140 mg total dose) will be administered by qualified study staff at each dosing visit during the 156-week open-label treatment epoch (ie, at Weeks 12, 16, 20, 24, etc.) and during the PTA-Open-Label Treatment Epoch (ie, at Weeks 168, 172, 176, 180 etc.). If and when 140 mg/mL pre-filled syringes become available during the Open-Label Treatment Epoch, the 140 mg dose may be administered by a single 140 mg/mL s.c. injection.

The investigational product dose is fixed and will not be adjusted for individual patients during the study. There are no temporal restrictions for study drug administration (e.g., proximity to meals, sleep or activity).

All kits of study treatment assigned will be recorded in the IRT. Novartis monitors will reconcile treatment assigned vs treatment administered and ensure that the information is congruent during their monitoring visits.

During the **COVID-19 pandemic** that limits or prevents on-site study visits, delivery of study drug directly to a patient’s home is generally permitted in the event the Investigator has decided that an on-site visit by the patient is no longer appropriate or possible, and that it is in the interest of the patient’s health to administer (e.g., self-injection or study staff administration at patients’

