2.1.1 General definitions

Study drug

Novartis will supply the investigational product listed below

- AMG 334 70 mg/1 mL pre-filled syringe
- Matching placebo in 1mL pre-filled syringe, identical in appearance

Two injections of AMG 334 70 mg (equaling 140 mg total dose) or placebo will be administered at each dosing visit. The matching Placebo to AMG 334 pre-filled syringe will have the same appearance as the investigational drug. Each syringe will be packaged individually in double blinded fashion for the double-blind treatment Epoch. The study treatments will be labelled as:

- AMG 334 70mg/1mL or Placebo for Double-Blind Treatment Epoch

Baseline

The baseline period for efficacy endpoints collected by the daily diary (e.g., monthly migraine days, acute migraine-specific medication days, MPFID, etc.) is defined as the period

between week -4 visit (when eDiary device is dispensed to the patient for daily data capture) and the day prior to study day 1 (study day 1 is not included).

A baseline for PRO ([REDACTED] MPFID) and safety (including C-SSRS) values refers to the last evaluable measurement prior to the first administration of the study drug, irrespective of re-screening. In this case, baseline values will be the values obtained on the day of the randomization (Day 1, Visit 101), or on an earlier visit (scheduled or unscheduled) which is the closest to Visit 101, if Visit 101 is missing or the assessment was not done at baseline.

Change from Baseline in Monthly Efficacy Measurement

The change from baseline in monthly efficacy measurement is the monthly efficacy measurement in the monthly interval prior to the given time point minus the baseline monthly efficacy measurement. Please, refer to the monthly intervals for efficacy endpoints defined in [Table 2](#). For example, change from baseline in monthly migraine days in the last month (month 3) of the double-blind epoch will be calculated based on the following:
(Monthly migraine days in the last month of the DBTE) – (monthly migraine days during the baseline phase)

If the baseline or post-baseline value is missing, then the change from baseline is set to be missing.

Percent Change from Baseline

The change from baseline divided by baseline and multiplied by 100:

$$(\text{post-baseline} - \text{baseline}) * 100 / \text{baseline}$$

50% (or 75%, 100%) response is defined as a decrease from baseline score value for at least 50% (or 75%, 100%).

Study day

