Study Day 1 is defined as the first investigational product (IP) dose date. For subjects who are randomized but not dosed after randomization, the Study Day 1 is defined as the date of randomization.

Study Day is defined as the number of days from Study Day 1.

Before Study Day 1:

$$\text{Study Day} = (\text{Date of Interest} - \text{Date of Study Day 1})$$

On or after Study Day 1:

$$\text{Study Day} = (\text{Date of Interest} - \text{Date of Study Day 1}) + 1$$

Therefore the day prior to Study Day 1 is -1.

Last date of patient contact

The date of last patient contact will be selected as the minimum of the following non-missing dates:

1. 'Date of Discontinuation/study phase completion', either from the study completion page or
2. The treatment epoch completion page if calculated specifically for a study epoch.

Duration of Migraine

The duration of migraine in years (migraine with aura or migraine without aura, whichever is earlier) is calculated by the following formula: current age (in years) - age at migraine onset (in years).

Current age is calculated by the following formula, the date of informed consent – birth date (at least the year).

If the current age calculated as detailed above or the age at migraine onset is missing then duration of migraine will be missing.

Duration of exposure to AMG 334

For all calculations of exposure, dose date refers to receiving dose > 0, but can include partial doses.

Duration of DB IP Exposure

If subject enters into the open-label treatment phase,

Duration = Minimum (Last DB Dose Date + 27, First OLTP Dose Date, EoS Date-1) – First DB Dose Date+1

Otherwise,

Minimum (Last DB Dose Date + 27, EoS Date) – First DB Dose Date+1

Duration of OL IP Exposure

Minimum (Last OLTE Dose Date + 27, EoS Date) – First OLTE Dose Date+1

Subject Incidence

The subject incidence for a given event in a given period is defined as the number of subjects with at least one reported occurrence of the event divided by the number of subjects who entered that period. For subjects with multiple occurrences of the same event, the event will only be counted once per subject.

Exposure-Adjusted Subject Incidence Rate

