Study visit	Target Day	Study Day for vital signs, C-SSRS (for lab [REDACTED] include only Day1, Week 12, 24, 64)	Study Day [REDACTED]
Baseline	Please refer to Section 2.1.1		
Day 1	1	1	1
Week 4	29	16-43	16-43
Week 8	57	44-71	44-71
Week 12	85	1.72 to (week 12 OLTE dose date) for subjects who receive OLTE dose at week 12 2.72-99 for subjects who did not receive OLTE dose at week 12	1.72 to (week 12 OLTE dose date) for subjects who receive OLTE dose at week 12 2.72-99 for subjects who did not receive OLTE dose at week 12

For safety analyses which are summarized by study phase, analysis windows will be set up based on study phase:

Table 4 Study Phases for Safety analysis

Study Phase	Start Time Point	End Time Point
Double-blind Treatment Epoch	Study Day 1 (after the 1st DB IP Dose)	
 • First OLTE Dose Date - 1 for subjects receive OLTE IP dose; • MIN(EoS Date, last IP dose date + 84 days) for subjects did not receive any OLTE IP dose

Note: all anti-AMG 334 antibody data during all epochs will be included in immunogenicity analysis.

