5.8 Appendix C: Criteria for ECG abnormalities

Table 13 ECG Abnormality Ranges

ECG Parameter	Abnormality Flags	
	Absolute	Relative*
RR Interval	Low: < 600 msec ; High: > 1200 msec	Low: ≤ -20%; High: ≥ 20%
PR interval	Low: < 120 msec ; High: > 200 msec	Low: ≤ -20%; High: ≥ 20%
QRS Interval	Low: < 60 msec ; High: > 109 msec	Low: ≤ -20%; High: ≥ 20%
QT Interval	Low: < 320 msec ; High: > 450 msec	Low: ≤ -20%; High: ≥ 20%
QTcB Interval (Bazett's correction)	Low: < 320 msec ; High: > 450 msec	Low: ≤ -20%; High: ≥ 20%
QTcF Interval (Fridericia's correction)	Low: < 320 msec ; High: > 450 msec	Low: ≤ -20%; High: ≥ 20%

*Relative change from previous measurement in percent (%)

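### The planned ECG incidence table does not separate abnormalities present before the first dose from new ones, and the relative ECG flags in SAP Table 13 are measured from the previous reading, not from the pre-dose baseline.

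*SAP*

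**What the plan says.** SAP 2.7.4 gives the whole ECG analysis in one line: "Subject incidence of abnormal ECG diagnosis will be summarized by treatment group separately for the DBTE". It describes the ECGs as routine safety monitoring, not as an assessment of QTc effect, and does not refer to Table 13.

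SAP 2.1.1 defines subject incidence as the "number of subjects with at least one reported occurrence of the event divided by the number of subjects who entered that period", each patient counting once. The double-blind safety phase (SAP Table 4) opens at "Study Day 1 (after the 1st DB IP Dose").

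For safety data, SAP 2.1.1 also says that baseline "values refers to the last evaluable measurement prior to the first administration of the study drug". SAP Appendix C (5.8), Table 13, gives each ECG interval an absolute range and a relative flag at a fall or rise of 20% or more. Its footnote defines the relative flag as "Relative change from previous measurement in percent".

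SAP Table 14 schedules ECGs at Screening, Day 1, Week 4 and Week 12.

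**The concern.** A safety table by arm should let the reader see what arose on treatment. Here a patient with a long-standing minor abnormality, seen again at Week 4, appears to count the same as a patient whose ECG became abnormal after dosing. Eligibility does not remove the problem: Protocol 4.2, exclusion criterion 16, bars only ECG abnormalities that carry a significant safety risk, so lesser ones can be present at entry.

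The SAP handles its other safety data differently. Laboratory values and vital signs are summarised as change from baseline (2.7.2, 2.7.5), the C-SSRS has a shift table (2.7.3), adverse events must be treatment-emergent (2.1.2), and treatment-induced antibodies are counted over patients negative at baseline (2.7.6.2). ECG has no equivalent.

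Table 13 raises a second, smaller question of the same kind: its reference is the preceding reading, although a pre-dose baseline is defined and available. Protocol 3.6 says that patients will be monitored for cardiovascular effects, so the ECG summary should be readable on this point.

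**Working it through.** The plan states no ECG figure, so there is none to reproduce. All rates in part 1 are assumptions.

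**1. Dilution of the incidence contrast**

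Let b be the share of patients abnormal before dosing, s the share of those seen abnormal again after dosing (taken as equal in both arms), and q the new-onset rate among the rest. The tabulated incidence in an arm is

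p = b·s + (1 − b)·q.

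The risk difference is (1 − b)(q1 − q0), whatever s is. Assume q1 = 6% and q0 = 3%, a true ratio of 2.0 and a true difference of 3.0 points. With s = 100%:

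| b | Active | Placebo | Ratio | Difference (points) |
|---|---|---|---|---|
| 0% | 6.0% | 3.0% | 2.00 | 3.0 |
| 10% | 0.10 + 0.90 × 0.06 = 15.4% | 0.10 + 0.90 × 0.03 = 12.7% | 1.21 | 2.7 |
| 20% | 0.20 + 0.80 × 0.06 = 24.8% | 0.20 + 0.80 × 0.03 = 22.4% | 1.11 | 2.4 |
| 30% | 0.30 + 0.70 × 0.06 = 34.2% | 0.30 + 0.70 × 0.03 = 32.1% | 1.07 | 2.1 |

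With s = 70% the ratio is 0.124/0.097 = 1.28 at b = 10% and 0.252/0.231 = 1.09 at b = 30%; the differences do not change. The ratio suffers most, while the difference shrinks only by the factor 1 − b. Counting new onset among patients not abnormal at the last pre-dose ECG gives back 6% v 3%.

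**2. Reference for the relative flags**

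At Week 4 the previous scheduled ECG is Day 1, which is the baseline, so the two rules agree. They can differ only at Week 12, where the previous scheduled reading is Week 4.

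- Two steps each just under 20% compound to just under 1.2 × 1.2 − 1 = +44%, or 0.8 × 0.8 − 1 = −36%, with no relative flag.
- PR 150, 175, 199 ms: 175/150 = +16.7% and 199/175 = +13.7%, so no relative flag, and all three values lie inside the absolute range of 120 to 200. From baseline the change is 199/150 = +32.7%.
- QTc 400, 440, 480 ms: steps of +10.0% and +9.1%, so no relative flag, but 480 exceeds the absolute limit of 450 and is flagged. A 20% rise from any QTc above 375 crosses that limit, since 375 × 1.2 = 450.

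The gap is therefore confined to gradual changes that stay inside the absolute limits.

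**3. Whether the Week 12 ECG is in the window**

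Table 4 ends the double-blind phase at "First OLTE Dose Date - 1 for subjects receive OLTE IP dose". Protocol 5.5.4 gives open-label doses "ie, at Weeks 12, 16, 20, 24, etc". Read literally, a Week 12 ECG taken on the day of the first open-label dose falls outside the phase. For those patients Week 4 is then the only scheduled ECG in the window, and the two reference rules coincide.

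**The case against.** The strongest reply is that the consequences are limited, and much of it stands.

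- The definition speaks of a reported occurrence and does not say expressly that a persisting, pre-existing finding counts. That is fair; but nothing excludes it either, so the text needs to settle it.
- Clinically significant ECG abnormalities are recorded as medical history, current condition or adverse event (Protocol 6.5.5), so new ones can reach the treatment-emergent event tables by arm. SAP 2.1.1 also provides for listings of all assessments. A reader might infer that the plan cannot show whether abnormalities arise on drug; these routes do not support so strong a statement. They do not replace the table: the first depends on a judgement of clinical significance, and a listing is not a summary by arm.
- Safety analyses carry no between-arm test (SAP 2.7), and precision is low anyway. With the planned 110 per arm, a test of an assumed 5% v 10% would have power of about 0.29 even with no pre-existing abnormality. This stands, but a descriptive table should still show on-treatment findings.
- A reader might infer that the previous-reading rule distorts the incidence table. The documents do not support this: 2.7.4 counts abnormal diagnoses, does not cite Table 13, and no section says that the relative flags are tabulated.
- Nor is stepwise drift always missed, because the absolute limits catch many cases. A QTc of 400, 500, 400 ms does draw a −20% flag on returning to baseline, but that patient was already flagged at 500 and would count only once.
- The theoretical risk in Protocol 3.6 concerns ischaemia, and the related secondary endpoint is cardiovascular events, not interval drift. This limits the weight of the second part.

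**Conclusion.** The point holds as a cheap improvement. As written, the ECG table does not separate old from new abnormalities, so the descriptive contrast can be diluted. Under the assumed 6% v 3% with full persistence, prevalence of 10% to 30% gives a ratio of 1.21 to 1.07 instead of 2.0, and a difference of 2.7 to 2.1 points instead of 3.0. With no pre-existing abnormality there is no dilution. Prevalence, persistence and new-onset rates are all assumptions; the documents give none of them.

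A reader might go further and infer that the table is biased in favour of one arm, or that a treatment effect will be hidden. Neither follows: randomisation balances pre-existing abnormalities in expectation, and the effect is attenuation of unknown size.

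The Table 13 reference is inconsistent with the SAP's own safety baseline, but its reach on scheduled ECGs is narrow (Week 12 only) and its effect on any reported table is not shown.

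**What to change.** In SAP 2.7.4, tabulate by arm either newly occurring abnormal ECGs among patients not abnormal at the last pre-dose ECG, or a shift table from baseline to worst post-dose ECG. In Table 13, compute relative change from the pre-dose baseline and state whether the flags are tabulated. In the same edit, state whether a Week 12 ECG taken on the day of the first open-label dose belongs to the double-blind phase.

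The scheduled ECGs already supply the data, and they are processed centrally (Protocol 8.3). The cost is a few lines of SAP text; the downside is one more table.
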